#### 7.1.3 Exploratory outcomes

- UMSARS score (Parts I and II) at 96 weeks;
- MSA-QoL scale at 96 weeks;
- UMSARS score (Parts III and IV) at 96 weeks;
- The use of Anti-parkinsonian or anti-orthostatic hypotension drugs at 96 weeks;
- The number of falls at 96 weeks;
- Patients reaching a score of 3 or more on UMSARS-I items 1 (speech), 2 (swallowing), and 8 (falling) at 96 weeks;
- CGI and MoCA scores at 96 weeks.

Serum will be collected at baseline and 12 weeks, 24 weeks, 36 weeks, 48 weeks and 96 weeks for biomarker analysis. CSF will be collected at baseline and 48 weeks for biomarker analysis. Further details on the scoring and ranges of all outcomes can be found in the Appendix.

### 7.1.4 Timing of outcomes

Table 1 provides an overview of primary and secondary outcomes and the time points at which they will be collected.

Table 1: Data collection measures and time points.

| Measure                      | 0 | 4* | 12 | 24 | 36 | 48 | 58* | 96 |
|------------------------------|---|----|----|----|----|----|-----|----|
| Screening measures           |   |    |    |    |    |    |     |    |
| Physical Examination         | ✓ |    | ✓  | ✓  | ✓  | ✓  |     | ✓  |
| Neurological Examination     | ✓ |    |    | ✓  |    | ✓  |     | ✓  |
| Vital Signs including weight | ✓ |    | ✓  | ✓  | ✓  | ✓  |     | ✓  |
| Fasting blood test           | ✓ |    |    | ✓  |    | ✓  |     |    |
| Eligibility confirmation     | ✓ |    |    |    |    |    |     |    |
| Primary outcome              |   |    |    |    |    |    |     |    |
| UMSARS Part 1, 3 and 4       | ✓ |    | ✓  | ✓  | ✓  | ✓  |     | ✓  |
| UMSARS Part 2                | ✓ |    | ✓  | ✓  | ✓  | ✓  |     | ✓  |
| Secondary outcomes           |   |    |    |    |    |    |     |    |
| MSA-QoL scale                | ✓ |    |    |    |    | ✓  |     | ✓  |
| MoCA                         | ✓ |    | ✓  | ✓  | ✓  | ✓  |     | ✓  |
| Serum collection             | ✓ |    | ✓  | ✓  | ✓  | ✓  |     | ✓  |
| CSF collection               | ✓ |    |    |    |    | ✓  |     |    |
| Other measures               |   |    |    |    |    |    |     |    |
| BDI-II                       | ✓ |    | ✓  | ✓  | ✓  | ✓  |     | ✓  |
| COMPASS Select               | ✓ |    |    | ✓  |    | ✓  |     | ✓  |
| COMPASS Change               |   |    |    | ✓  |    | ✓  |     | ✓  |
| Timed Motor Tests            | ✓ |    |    | ✓  |    | ✓  |     | ✓  |
| The Unified Dystonia Rating  | ✓ |    | ✓  | ✓  | ✓  | ✓  |     | ✓  |
| IMP administration           | ✓ |    |    | ✓  | ✓  | ✓  |     |    |
| Adverse Events/SAEs review   | ✓ | ✓  | ✓  | ✓  | ✓  | ✓  | ✓   |    |
| Concomitant Medication       | ✓ | ✓  | ✓  | ✓  | ✓  | ✓  |     |    |

\*: Telephone call

## 7.2 Primary outcome Analysis

The primary outcome is the total Unified Multiple System Atrophy Rating Scale (UMSARS) score (Parts I and II) at 48 weeks. The primary analysis will compare exenatide patients to be best medically treated patients using a two-level mixed model that includes the total UMSARS scores from four time-points (12 weeks, 24 weeks, 36 weeks and 48 weeks) with interaction terms between the intervention and time-point indicator variables to enable estimation of the effect of intervention at 48 weeks. This model will also adjust for baseline UMSARS score and MSA subtype using fixed effects.

In detail, the primary analysis will involve fitting the model

$$UMSARS_{ij} = \beta_0 + \beta_1 TRT_i + \beta_2 j TIME_j + \beta_3 j TRT_i \times TIME_j + \beta_4 UMSARS0_i + \beta_5 MSA_i + u_i + \epsilon_{ij}$$

to patients  $i = 1, \dots, 48$  and time-points  $j = 12, 24, 38$  and 48 weeks, where  $UMSARS_{ij}$  and  $UMSARS0_i$  are the UMSARS total scores for patient  $i$  at time-point  $j$  and baseline respectively,  $TRT_i$  is the intervention group indicator (0=standard; 1=Exenatide),  $TIME_j$  are time-point indicators,  $MSA_i$  is a MSA subtype indicator, and  $u_i \sim N(0, \sigma_u^2)$  and  $\epsilon_{ij} \sim N(0, \sigma^2)$  are error terms. All modelling assumptions will be checked.

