A small, “proof-of-concept” open-label phase 2 clinical trial evaluating the safety and efficacy of Exenatide in PD which showed a significant improvement in motor scores and cognitive efficiency at 12 months in patients with PD treated with Exenatide compared to a control group, which persisted following drug withdrawal (Aviles-Olmos et al. 2013, 2014). Despite the open-label design, this study demonstrated that a drug in clinical use for another medical condition could be successfully tested for its disease-modifying effects in patients with PD using standard clinical measures, without the need to include a placebo-controlled arm, in a relatively inexpensive way. The aim of the open label trial was to provide proof of concept of possible efficacy to reassure investment into more formal double blind placebo controlled efficacy trials.

Following on from this, a fully randomised, placebo-controlled trial of Exenatide in patients with moderate stage PD was conducted, which replicated the results of the previous open label trial and showed Exenatide reduced motor severity of PD compared to placebo. Exenatide was well-tolerated in this patient group and it was shown for the first time that peripherally administered Exenatide crossed the blood brain barrier and is detectable in the cerebrospinal fluid at a ratio of around 3% of that detected in serum (Athauda et al. 2017). Post hoc analysis also indicated possible beneficial effects on depression which can be a major contributor to morbidity in both PD and MSA (Athauda et al. 2018). Using patient serum, we isolated and analysed neuronal derived exosomes to assess target engagement and demonstrated that Exenatide appears to normalise brain insulin signalling with subsequent activation of downstream effectors Akt and mTOR (Athauda et al. 2019).

These encouraging results have set the ground for translation into early clinical trials of Exenatide in further neurodegenerative diseases.

Clinical trials in MSA can be conducted with smaller group sizes, due to the marked faster disease progression of MSA compared with that of PD (Fernagut et al. 2014). In addition, previous studies have demonstrated a consistent rate of progression in the Unified Multiple System Atrophy Rating Scale (UMSARS) Part II (Motor examination) (Wenning et al. 2004, 2013; Low et al. 2015; Dodel et al. 2010; Poewe, Hauser, and Lang 2015; Low et al. 2014)

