8.3 Treatment Schedule

For participants randomised to receive the trial drug they will receive 2mg Exenatide once-weekly for 48 weeks via subcutaneous injection. Astra-Zeneca announced that they will discontinue manufacturing of Bydureon from March 2021 and that this would be replaced by

the Bydureon BCise. There is no difference to the dose of exenatide contained between the devices. Patients who have already started on Bydureon will be reconsented and given new instructions about how to use the updated device.

The first dose will be administered in clinic following injection teaching and the patient will be given sufficient number of pens to continue injections until their 12 week follow up visit. Each participant will be shown an online video instruction specifically for the Bydureon or Bydureon BCise pen injections, which they can revisit as necessary. Each subsequent injection will be given every 7 days at home by self-administration. Injections will be given into the abdomen, arm, thigh or buttocks. Participants will be given a dosing diary to record the time and day of all injections administered.

The control group of patients are very important in view of the continued but variable rate of the neurodegenerative process of MSA.

Patients will continue to see their treating neurologist at normally scheduled appointments. Adjustment to MSA medications will be permitted based on the clinical judgement of the treating neurologist and/or the clinical trial team to optimise symptom control throughout the duration of the trial. Doses of all medications will be recorded at each trial visit.

8.3.1 *Dose Modifications*

Patients experiencing abdominal pain consistent with a clinical diagnosis of pancreatitis will receive investigation and treatment according to NHS standard of care and the trial medication will be stopped pending confirmation or exclusion of the diagnosis. Confirmation of a diagnosis of acute pancreatitis will result in the trial medication being permanently stopped.

Patients found to have an elevation in serum Amylase (>50% above baseline and >50% above the laboratory reference range) will have a clinical assessment and have the test repeated after 1 week. If the amylase remains elevated, a clinical decision will be made whether to temporarily withdraw exenatide until the amylase return to the normal range or permanently withdraw exenatide.

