- Concomitant Medication: All over-the-counter or prescription medication, vitamins, and/or herbal supplements will be recorded.

- The Montreal Cognitive Assessment is a 30-point test that assesses several cognitive domains to detect cognitive impairment.
- The Beck's Depression Inventory-II is a patient rated depression severity scale.
- The Unified MSA Rating Scale (UMSARS) is a multidimensional, reliable, and valid scale for semi quantitative assessment of MSA patients with high internal consistency and substantial-to-excellent interrater agreement and is sensitive to change. It focuses on all aspects of the disorder, including autonomic, cerebellar, and parkinsonism manifestations. USMARS has an Activities of Daily Living score (UMSARS Part 1, 12 questions); a Motor Examination score (UMSARS Part 2, 14 questions); Autonomic examination score (UMSARS Part 3) and a global disability scale (UMSARS Part 4). Part 2 will be videotaped to ensure there is the option to retrospectively score the participants by blinded raters if there are concerns regarding bias in view of this being an open label trial. All videos will be stored in an appropriate secure encrypted storage facility which can only be accessed by members of the research team.
- The Composite Autonomic Symptom (COMPASS) Select is a subset of the full COMPASS consisting of 46 questions in 5 domains (orthostatic intolerance, secretomotor, bladder, constipation, and sleep), leading to a total score between 0 and 125, with a higher score indicating greater impairment
- The COMPASS Change Scale is a derivation of COMPASS-select in which the participants score their change in autonomic symptoms since their last exam. It comprises 26 retrospective questions in which participants scored how much their autonomic symptoms had changed. It is divided into change of 6 autonomic function domains (or 5 in women) [i.e. orthostatic intolerance, sexual failure (erectile dysfunction, male only), bladder disorder, secretomotor disorder, constipation and sleep disorder] with a maximum score of 160 for men and 150 for women (Wenning GK et al., 2007).
- MSA-QoL scale is a validated 40 item self-completed questionnaire in which a participant is asked to record the problems due to their MSA over the preceding 4 weeks.
- Timed Motor Tests include a hand tapping task to evaluate the number of hand taps that an individual can perform within 30 seconds and a timed, sit, stand, walk task.

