11.4 Statistical analysis plan

11.4.1 *Summary of baseline data and flow of participants*

A CONSORT diagram will be used to describe the course of patients through the trial. Baseline characteristics will be summarised by randomised group. Summary measures for the baseline characteristics of each group will be presented as mean and standard deviation for continuous (approximate) normally distributed variables, medians and interquartile ranges for non-normally distributed variables, and frequencies and percentages for categorical variables. The impact of missing data and non-compliance will be investigated.

11.4.2 *Primary outcome analysis*

The primary outcome will be the difference in total Unified Multiple System Atrophy Rating Scale (UMSARS) score (Parts I and II) at 48 weeks. The primary analysis will compare exenatide patients to be best medically treated patients using a regression (ANCOVA) model that adjusts for baseline severity and MSA subtype. All modelling assumptions will be checked. The statistical analysis will be based on all participants as randomised, irrespective of subsequent compliance with allocated treatment (intention to treat analysis). The impact of missing data and non-compliance will be investigated as appropriate.

11.4.3 *Secondary outcome analysis*

Key secondary outcomes would include loss of independent ambulation by end of study, defined by a score of 4 or more in UMSARS-I item 7 (walking); MSA-QoL scale UMSARS parts I, II, III and IV at week 48 and 96; use of anti-parkinsonian or anti-orthostatic hypotension drugs; number of falls; and the proportion of patients reaching a score of 3 or more on UMSARS-I items 1 (speech), 2 (swallowing), and 8 (falling); clinical global impression (CGI) at week 48 and 96; MoCA scores at week 48 and 96. These outcomes will be analysed using appropriate statistical methods, adjusting for baseline values where possible. Again, all assumptions will be checked.

11.4.4 *Sensitivity and other planned analyses*

Sensitivity analyses will be performed to identify differences between patients who drop-out or have missing data and patients with complete data for each variable.

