#### 4.3 Sample size

The recent rasagiline for MSA (MSA-Ras) trial evaluated rasagiline versus placebo using the UMSARS total (Parts I and II) as the primary efficacy measure after 48 weeks treatment. Patients in the placebo group declined by mean 7.8 points (SD 10.4 – Werner et al. 2015).

Therefore, on the basis of this previously collected data and with a two-sided 5% significance level, we estimated that a sample size of 40 patients (20 per group) would be required to detect a difference of 5 total UMSARS points between the two groups, assuming a correlation between baseline and final disease severity of 0.85. These calculations were based on a common SD of 10.4, 80% power and an

overall type 1 error rate of 5%. A 5-point difference between groups would be a clinically important effect size. Based on a 20% dropout rate as reported from previous trials, the sample size would be 50 (25 per arm).

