## 7.5 Sensitivity analyses

Several sensitivity analyses will be performed for the primary outcome. These are:

- The effect of the intervention will be assessed using a single-level linear regression model, adjusted for MSA subtype and baseline severity.
- If adherence is deemed to be an issue, per-protocol and complier average causal effect (CACE) analyses will be performed.

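### The primary mixed model assumes the same variance at every visit, so its week-48 standard error is too small if patients progress at different rates

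*SAP*

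**What the plan says.** SAP 7.2 analyses the primary outcome "using a two-level mixed model that includes the total UMSARS scores from four time-points (12 weeks, 24 weeks, 36 weeks and 48 weeks"), with treatment-by-visit terms so that the effect can be read at week 48. Baseline UMSARS and MSA subtype enter as fixed effects. The formula contains a random intercept with variance σ_u² and a residual with a single variance σ². It has no random slope, visit-specific variance, unstructured covariance or robust standard error. After defining the two terms, the section says that they "are error terms. All modelling assumptions will be checked". It names no criterion and no replacement model. Neither the estimation method (ML or REML) nor the degrees of freedom are stated.

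Protocol 11.4.2 specified a different primary analysis, "using a regression (ANCOVA) model that adjusts for baseline severity and MSA subtype". In the SAP this becomes a sensitivity analysis (7.5): "The effect of the intervention will be assessed using a single-level linear regression model, adjusted for MSA subtype and baseline severity". SAP 8 notes the use of four time-points but does not regard it as a major change.

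On progression, Protocol 8.3 refers to the "continued but variable rate of the neurodegenerative process of MSA". Protocol 3 says that "previous studies have demonstrated a consistent rate of progression" in UMSARS Part II.

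**The concern.** A random intercept with one residual variance forces equal variance at weeks 12, 24, 36 and 48, and equal correlation between every pair of visits. The visit indicators absorb the average decline, so that is not the difficulty. The difficulty is variation between patients in the rate of decline. If rates differ, variance given baseline grows with time and is largest at week 48. The model averages it with three smaller variances, so it understates uncertainty most at the visit that carries the primary result.

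SAP 5.1 sets a 5% significance level and 95% intervals. Protocol 5.1 intends encouraging results to support a funding application for a larger trial. An interval that is too narrow would make the evidence look firmer than it is.

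**Working it through.** **Inputs.** From Protocol 11.2.1 and SAP 4.3: common SD 10.4, baseline-to-final correlation 0.85, difference 5 points, 80% power, two-sided 5%, 20 evaluable per arm, 50 randomised. From SAP 7.2: the model and its four visits. The documents give no slope variance, visit-error SD or correlation between visits. These are assumed and varied.

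**1. The plan's own figure.** Residual SD given baseline = 10.4 × √(1 − 0.85²) = 5.48, variance 30.0. Patients per arm = 2 × (1.96 + 0.84)² × 30.0 / 5² = 18.8, so 19. With 20 per arm, power is 80.2% (t, 36 df). Then 40 / 0.8 = 50. The stated size reproduces for a week-48 ANCOVA.

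**2. Shortfall in the standard error.** Let f be the share of week-48 variance, given baseline, that comes from differing slopes. Relative variance at week t is v(t) = (1 − f) + f(t/48)². With complete data the model uses the mean of v over the four visits. The mean of (t/48)² is (1/16 + 4/16 + 9/16 + 16/16)/4 = 0.469. Hence model SE / true SE = √(1 − 0.531f), and large-sample type I error = 2[1 − Φ(1.96 × ratio)].

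| f | SE ratio | Type I error |
|---|---|---|
| 0 | 1.00 | 5.0% |
| 0.25 | 0.93 | 6.8% |
| 0.50 | 0.86 | 9.3% |
| 0.75 | 0.78 | 12.8% |
| 0.93 | 0.71 | 16.3% |
| 1 | 0.685 | 18.0% |

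If all the variance grows linearly instead (a random walk), the mean is (1 + 2 + 3 + 4)/16 = 0.625, the ratio is 0.79 and type I error is 12.1%.

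**3. What the plan's inputs allow.** Variance of change = 10.4² × 2 × (1 − 0.85) = 32.4 (SD 5.70). This equals the variance due to slopes over 48 weeks plus twice the visit-error variance. Slope variance is therefore 2 × (16.22 − error variance), and error SD cannot exceed √16.22 = 4.03. At that limit slopes do not vary and the SAP model is correct. If 10.4 is read as the SD of the 7.8-point decline, the limit is 10.4/√2 = 7.4.

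**4. Simulation at the plan's inputs.** No treatment effect, 20 per arm, complete data, linear slopes, 6,000 trials per setting. REML uses Satterthwaite t; ML uses z.

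| Assumed visit-error SD | Slope share of week-48 residual variance | Mean REML SE / empirical SD | REML, t | ML, z |
|---|---|---|---|---|
| 1 | 94% | 0.71 | 16% | 19% |
| 2 | 77% | 0.78 | 12% | 15% |
| 3 | 46% | 0.88 | 8% | 10% |
| 3.5 | 26% | 0.93 | 6% | 8% |
| 3.9 | 7% | 0.98 | 5% | 7% |

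At error SD 2 the estimate's empirical SD is 1.745, the mean REML SE is 1.355 and the ANCOVA SE is 1.742. The 95% half-widths are about 2.7 points (SAP model) and 3.5 points (ANCOVA). An observed difference between those two could be significant by the primary model only.

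**5. Variations.**
- 10.4 as the SD of change, with an assumed baseline SD of 15 and error SD 1 to 7: REML/t 17, 16, 14, 12, 9, 7, 6%; ML/z 20, 19, 17, 14, 12, 9, 7%.
- Random walk instead of linear slopes: at most 12% (REML/t) and 14% (ML/z).
- 25 per arm: within about 1 percentage point, up to about 2 in one random-walk setting.
- 25 per arm, about 18% dropout missing at random, plan's inputs, 1,200 trials per setting. Error SD 2: SAP model 14.0% (REML/t) and 15.6% (ML/z), unstructured REML/t 5.1%, completer ANCOVA 4.7%. Error SD 3: 8.7%, 11.0%, 5.2% and 5.2%.
- The extreme f = 1 with 20% random dropout, 50 randomised: 19.6% (REML/t) and 22.2% (ML/z).

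With complete data, week-48 ANCOVA gave 4.4–5.5% in every setting of step 4 and of the first two variations.

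**The case against.** The plan's SD and its statement "assuming a correlation between baseline and final disease severity of 0.85" are exactly compatible with the SAP model if visit-error SD is 4.03, so no figure in the documents contradicts it. The remark about a variable rate explains why a control group is needed and does not say that the variation is between patients. The top of the range needs a visit-error SD near 1 point, a reliability of 1 − 1²/10.4² = 0.99. Protocol 8.6 claims only "substantial-to-excellent interrater agreement". An assumed reliability of 0.89–0.94 (error SD 3.5–2.5) gives roughly 7–10% with REML/t. The 17% and 20% maxima also use a baseline SD of 15 that is not in the plan. Finally, the point estimate is unbiased with complete data, assumption checks are promised, the regression in SAP 7.5 would show a discrepancy, and SAP 8 discloses the four time-points.

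Most of this stands as a limit on size: the inflation is conditional, and moderate values are more plausible than the extremes. It does not remove the problem. Nominal error requires essentially no slope variation, and the consistent rate cited for Part II may mean consistency across studies. A check with no stated consequence leaves any switch to be chosen after the data are seen, and a supportive analysis does not alter the primary p-value or interval.

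**Conclusion.** The concern holds. The covariance in SAP 7.2 is safe only if patients do not differ in rate of progression. Otherwise it errs towards too small a standard error at week 48. Type I error is about 5–17% with REML and t, or 6–20% with ML and z. When slopes supply about half (46–55%) of the week-48 residual variance it is 8–9% or 10–12%. These figures rest on assumed visit-error SDs and, mainly, on linear slopes with complete data. At the most extreme setting dropout takes them slightly higher. What is affected is the standard error, interval and p-value. This should be fixed before analysis; confidence is medium because the governing inputs are not in the documents.

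**What to change.** Amend SAP 7.2 in one of two ways:

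- **(a)** Specify an unstructured covariance across the four visits, fitted by REML with Kenward-Roger or Satterthwaite degrees of freedom, and name a fallback if it does not converge, for example week-48 ANCOVA.
- **(b)** Restore the protocol's week-48 ANCOVA as primary and keep the mixed model as the sensitivity analysis.

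State the estimation and degrees-of-freedom method either way, and record the choice in SAP 8. In the same edit, reconcile time-point 38 in the formula with week 36, and define the patient index by the ITT population of SAP 5.3 instead of a fixed 48. Neither of these two points affects the result above.

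The cost is SAP wording and one line of code. Option (a) estimates ten covariance parameters (4 × 5 / 2) instead of two. Option (b) leaves patients without a week-48 score out of the primary fit. Either gives a wider interval when slopes vary.

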## 7.3 Secondary outcome analyses

The effect of the intervention on secondary outcomes will be assessed using appropriate single-level regression models, i.e. linear regression models for numerical outcomes, logistic regression models for binary outcomes, and Poisson models for count outcomes (or negative binomial models, if their use is indicated). All models will be adjusted for MSA subtype; models for numerical outcomes will also be adjusted for baseline outcomes if available. All analyses of secondary and other outcomes should be considered as supportive analyses.

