11.2 Sample size and recruitment

11.2.1 Sample size calculation

The recent rasagiline for MSA (MSA-Ras) trial evaluated rasagiline versus placebo using the UMSARS total (Parts I and II) as the primary efficacy measure after 48 weeks treatment. Patients in the placebo group declined by mean 7.8 points (SD 10.4 – Werner et al. 2015).

Therefore, on the basis of this previously collected data and with a two-sided 5% significance level, we estimated that a sample size of 40 patients (20 per group) would be required to detect a difference of 5 total UMSARS points between the two groups, assuming a correlation between baseline and final disease severity of 0.85. These calculations were based on a common SD of 10.4, 80% power and an overall type 1 error rate of 5%. A 5 point difference between groups would be a clinically important effect size. Based on a 20% dropout rate as reported from previous trials, the sample size would be 50 (25 per arm).

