#### 7.1.2 Secondary outcomes

- Patients with loss of independent ambulation by the end of the study, defined by a score of 4 in UMSARS-I item 7 (walking);
- Multiple System Atrophy health-related Quality of life (MSA-QoL) scale at week 48;
- UMSARS score (Parts III and IV) at week 48;
- Anti-parkinsonian or anti-orthostatic hypotension drugs comparing exenatide at week 48;
- The number of falls at week 48;
- Patients reaching a score of 3 or more on UMSARS-I items 1 (speech), 2 (swallowing), and 8 (falling) at week 48;
- Clinical global impression (CGI) at week 48;
- Montreal Cognitive Assessment (MoCA) scores at week 48;
- Safety of exenatide in MSA based on Adverse event reporting.

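### SAP 7.3 limits baseline adjustment to numerical secondary outcomes, although the protocol sets no such limit, so collected item scores go unused in the binary and count models

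*SAP*

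**What the plan says.** Protocol 11.4.3 lists the secondary outcomes together: the walking milestone, quality of life, UMSARS parts, drug use, falls, the speech, swallowing and falling milestones, CGI and MoCA. It then says they will be analysed by suitable methods, "adjusting for baseline values where possible".

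SAP 7.3 names three classes of model: linear for numerical outcomes, logistic for binary, and Poisson or negative binomial for counts. All are adjusted for subtype. Baseline enters only one class: "models for numerical outcomes will also be adjusted for baseline outcomes if available". SAP 7.4 carries the same models to the exploratory 96-week outcomes. SAP section 8 reports no major change from the protocol and mentions only the use of four time-points in the primary model.

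The binary outcomes affected are the walking milestone (item 7) and, in SAP 7.1.2, "Patients reaching a score of 3 or more on UMSARS-I items 1 (speech), 2 (swallowing), and 8 (falling) at week 48". The count outcome is the number of falls. UMSARS Part I and concomitant medication are both recorded at the baseline visit (Protocol 8.1; SAP Table 1).

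**The concern.** The SAP is narrower than the protocol and does not say so. The information left out exists: exclusion criterion 3 in Protocol 7.3 admits grades 0-2 on items 1, 2 and 8 and grades 0-3 on item 7. One patient may therefore be a single grade from the milestone and another three or four grades away, yet apart from subtype the model treats them alike. Randomisation is stratified by subtype only, so neither design nor analysis handles starting grade.

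At stake are some precision in the milestone, drug-use and falls comparisons, and protection against a chance imbalance in starting grade in an arm of about 25. Protocol 5.1 intends encouraging results to support an application for a larger trial, so these comparisons will be read.

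**Working it through.** **1. The plan's own figure.** The documents give no sample size for any secondary outcome. The primary calculation (Protocol 11.2.1) uses SD 10.4, a 5-point difference, two-sided 5% and 80% power, "assuming a correlation between baseline and final disease severity of 0.85".
- Without baseline: n = 2 x (10.4 x (1.960 + 0.842) / 5)^2 = 67.9, so 68 per arm.
- With baseline: 67.9 x (1 - 0.85^2) = 67.9 x 0.2775 = 18.85, so 19 per arm by the normal approximation and 20 by the t distribution (power 80.2%).
- Dropout: 40 / (1 - 0.20) = 50.

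The figure reproduces, and it depends on baseline adjustment.

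**2. Is adjustment possible?**

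| Outcome | Baseline version of the outcome | Usable baseline covariate |
|---|---|---|
| Items 1, 2, 8 at 3 or more | Constant (excluded at entry) | Item score 0-2 |
| Item 7 at 4 | Constant (excluded at entry) | Item score 0-3 |
| Drug use (yes/no) | Recorded | Baseline use |
| Drug dose | Recorded | Already covered, as numerical |
| Number of falls | None scheduled | Item 8 score, as a proxy |

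**3. Chance imbalance.** The SD of a standardised baseline difference is sqrt(2/n): 0.316 at 20 per arm and 0.283 at 25. A difference above 0.3 SD has probability 34% (29% at 25 per arm), and above 0.5 SD 11% (8%). If 35% start at grade 2 (assumed), the arms differ by 20 percentage points or more at that grade in 25% of trials at 20 per arm and 18% at 25.

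As an illustration, take logit(risk) = -3.5 + 2.0 x grade. Risk is 0.62 at grade 2 and 0.18 at grade 1. Moving 20 points of one arm from grade 1 to grade 2 shifts its risk by 0.20 x (0.62 - 0.18) = 0.09.

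**4. Power, ordinary logistic regression.** Likelihood-ratio test, 3,000 runs per scenario, subtype in every model, baseline grades 0/1/2 at 25/45/30%. Event rates and the latent correlation r between item and outcome are assumptions. Entries are power without -> with the item.

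| Per arm; rates | Events | r = 0.3 | r = 0.5 | r = 0.7 |
|---|---|---|---|---|
| 20; 50% v 20% | 14 | 55 -> 57% | 55 -> 63% | 57 -> 72% |
| 20; 40% v 10% | 10 | 63 -> 65% | 65 -> 72% | 63 -> 78% |
| 20; 30% v 10% | 8 | 38 -> 40% | 39 -> 45% | 40 -> 52% |
| 25; 50% v 20% | 17.5 | 64 -> 67% | 64 -> 70% | 65 -> 81% |

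At 20 per arm the gain is about 2, 6-8 and 12-15 points. At 30% v 10% and r = 0.7, (quasi-)separation rises from 14% to 33% of fits, so that row is the least reliable. With equal rates and 20 per arm, the test rejects in 5.0-7.4% of runs without the item and 6.3-7.9% with it.

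**5. Power, Firth-penalised regression.** Log-odds effect -1.5, grades at 25/40/35%, several independent sets of runs, about 7-10 events.

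| Patients | logit = -2.5 + 1.2 x grade | logit = -3.5 + 2.0 x grade |
|---|---|---|
| 40 | 32 -> 34%; 34 -> 34% | 28 -> 31%; 32 -> 35% |
| 50 | 39 -> 41%; 43 -> 43% | 34 -> 41%; 35 -> 42%; 42 -> 45% |

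The gain is 0-3 points at 40 patients. At 50 it is 0-2 points for the moderate slope and 3-7 for the steep one. Null rejection was 3.5% without and with the item under the moderate slope, and 6.0% without and 5.0% with it under the steep one.

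**6. Falls.** Negative binomial with robust SE, mean 4, rate ratio 0.4, 20 per arm, log-rate slope 0.3 / 0.6 / 0.9 per SD of the item (all assumed). The SE of the log rate ratio falls from 0.32, 0.35 and 0.39 to 0.31 in each case, and power goes 82 -> 84%, 74 -> 85% and 65 -> 82%. Null rejection was 7-11%, so the SEs are the safer guide.

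**The case against.** The best defence is that the protocol's rule applies only where adjustment can be done. Since no eligible patient has reached a milestone at entry, the outcome's own baseline value carries no information; the item grade is a different covariate, which the protocol does not name. That makes a clear breach arguable. It does not explain why drug use, which does vary at baseline, is left out, or why the narrowing is undeclared.

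The remaining points stand. No baseline fall count is scheduled, so item 8 is only a proxy. Drug use analysed as a levodopa-equivalent dose (Protocol 6.5) is numerical and already covered. With 7-8 events and three terms (treatment, subtype, item), there are fewer than three events per term, so a sparse model is a defensible choice. Adding the item also makes the odds ratio conditional on it.

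A reader might infer that the planned test credits chance imbalance to treatment and so produces false positives. The documents do not support that. Under randomisation, chance imbalance is already part of the sampling error, and in the logistic runs rejection under no effect was no lower overall with the item than without it. The 9-point shift is what one chosen imbalance does under one assumed slope; it is not an expected bias.

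**Conclusion.** The mismatch between SAP 7.3 and Protocol 11.4.3 is real and undeclared. Its consequence is modest: some precision is left unused, and imbalance in starting grade goes unadjusted in the binary and count models.

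The size rests on event rates, fall rates and prognostic strength that the documents do not give. A gain of about 0-4 points of power is realistic with a weak to moderate item or very few events. About 6-15 points needs a moderately to strongly prognostic item and more events. Those larger figures come mainly from ordinary logistic fits, so the lower range is the better expectation for the penalised analysis proposed here.

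It would go too far to conclude that the milestone analyses are invalid, that a large power loss is established, or that item grade is known to be the strongest predictor. SAP 7.3 calls these analyses supportive, and the primary model keeps both baseline and subtype, so the primary conclusion does not change.

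**What to change.** Amend SAP 7.3, and so 7.4, to state that:
- each binary milestone model adjusts for its own baseline item score as one linear term, plus MSA subtype;
- drug use as a yes/no outcome adjusts for baseline use (dose, if numerical, is already covered);
- the falls model adjusts for baseline item 8, named as a proxy because no baseline fall count is scheduled;
- logistic models use Firth's penalised likelihood, because events will be few;
- a standardised risk difference is reported beside the conditional odds ratio.

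Record the change in SAP section 8. If the sponsor prefers the present models, section 8 should instead state and justify the departure from Protocol 11.4.3.

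The cost is a few sentences and no new data. The downsides are one more term with few events, a different estimation method, and an odds ratio that is conditional on starting grade.
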